Presence of beards	Beards interfere with the fit of the Vo2 mask. Therefore, participants with beards will be asked to shave prior to their visit. If they are unwilling to shave, they will not be eligible for the study.
Claustrophobia	Participants who have been diagnosed or treated for claustrophobia will be excluded. Claustrophobia is a contraindication of the CPET test.
Currently experiencing symptoms of COVID-19 or < 7 days since last symptoms	Participants will be screened for COVID-19 symptoms using the BSW COVID-19 screener; if participants have past history of COVID-19 based on laboratory testing, participants will be ineligible if <7 number of days since last symptoms

Study Procedures

Phase I & II Subject Recruitment

Up to 100 participants (50 for each phase) will be recruited from Baylor Scott & White Sports Therapy and Research at The Star in Frisco, Texas through approved fliers, calls, emails, and social media, as well as through local community organizations, healthcare clinics, and collaborating centers and organizations, including but not limited to the Sports Academy and the University of North Texas. IRB-approved fliers will be posted at BSW The Star and at affiliated organizations and collaborators in the DFW Metroplex and surrounding areas. In addition, members of the study team will attend meetings with local clinicians and community partners to inform them of the purpose of the study. The study flier will contain information on the study and methods to contact the study team including (1) a QR code linked to the eligibility screener which will be stored in a REDcap, a HIPAA-compliant (21 CFR Part 11) secure web application, (2) a phone number, and (3) an email address of the study coordinator. Interested individuals may contact the study team by phone or email to learn more about the study and undergo a telephone screener or follow the QR code to complete the eligibility screener electronically. A snowball sampling technique will be used for further recruitment whereby interested participants will be invited to ask other athletes they know to contact the study team about participation. Eligible individuals will be contacted by a member of the study team to schedule their first study visit. It is anticipated that recruitment will take 2-4 weeks during each phase to achieve our desired sample size.

Subject Information and Screening

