Participant characteristics will be summarized with means and standard deviations or medians and interquartile ranges for numerical variables, and counts and percentages for categorical variables. The primary outcomes, VO₂ max and test duration, will first be assessed for normality using a Kolmogorov-Smirnov test prior to determining the analysis to be used. If the distribution meets the normality assumption, paired t-tests will be used to determine if there is a difference between participants when wearing and not wearing a face covering. If the distribution does not meet the normality assumption, Wilcoxon signed-rank tests will be used. All secondary outcomes will follow the same analysis plan of assessing the normal distribution assumption to determine the appropriate test for each outcome. Inter-rater reliability analysis will be conducted for the Attitudes for Face Coverings Questionnaire. All analysis will be performed using SAS 9.4 at a 0.05 significance level.

Risks & Benefits

- Physical risks: The potential risks include any and all risks associated with exercise including muscular injury, increased blood pressure and heart rate, and cardiac arrest. Other risks include hypoglycemia post-exercise and lightheadedness or syncope. Although some risks are unavoidable, the careful monitoring of signs and symptoms by the subject and clinical staff will minimize these risks.
- No psychological risks have been identified by participating in this study.
- No social risks have been identified by participating in this study.
- No economic risks have been identified by participating in this study.
- No legal risks have been identified by participating in this study.
- Potential benefits: Participants in this study may experience greater confidence in performing aerobic activities and may gain a better understanding of their personal functional exercise capacity at the time of testing. Participants may also better understand their body's response to exercise with and without a face covering which may impact training and performance in recreational and occupational ventures.

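### A normality test described as run on the outcomes, not on the within-person differences, chooses between paired t-test and Wilcoxon outcome by outcome, so the quantity being tested is left to the data

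*Combined protocol and SAP*

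**What the plan says.** The rule is in the Data Analysis section of the combined protocol and SAP. The two named primary outcomes "will first be assessed for normality using a Kolmogorov-Smirnov test prior to determining the analysis to be used". Then: "If the distribution meets the normality assumption, paired t-tests will be used" and "If the distribution does not meet the normality assumption, Wilcoxon signed-rank tests will be used". The choice is repeated for the rest: "All secondary outcomes will follow the same analysis plan of assessing the normal distribution assumption to determine the appropriate test for each outcome". The level is given once: "All analysis will be performed using SAS 9.4 at a 0.05 significance level".

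The section does not mention within-person differences. It does not say whether the distribution checked is the one with the covering, without it, pooled, or by sex. It names no default test, no effect measure and no confidence interval.

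Three other places bear on this. Phase I & II Subject Recruitment gives the size: "Up to 100 participants (50 for each phase) will be recruited". Research Design and Methodology makes each participant their own control in a two-test crossover with 1:1 randomised order. The same section promises, for both phases, a within-subjects analysis stratified by sex, which Data Analysis does not carry forward.

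**The concern.** Two things are wrong with the rule.

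- **The quantity checked.** A paired t-test uses only the differences d = (with covering) − (without covering). The shape of the outcome values is dominated by variation between people, which cancels in d. A check on the outcome values can therefore miss badly behaved differences and react to features, such as a gap between men and women, that do not affect the test.
- **The quantity tested.** The paired t-test concerns the mean of d; the signed-rank test concerns its pseudo-median (symmetry about zero). These coincide only if d is symmetric. Because the choice is made separately for each outcome, VO₂ max and duration could be reported against different targets.

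Skewed differences are plausible. The CPET procedures let a test stop for symptoms, pain, the participant's wish, or a top Borg score, so a few people stopping much earlier with the covering would give d a long tail. The documents do not show that this will happen.

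At stake is whether a reader can know beforehand what the main comparison of each outcome estimates.

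**Working it through.** The plan has no power calculation, SD or effect size to reproduce, so the stated rule was simulated.

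**From the documents:** n = 50 per phase; α = 0.05; Kolmogorov-Smirnov gate; paired t or signed-rank.

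**Assumed:** two-sided tests; gate at 0.05 with estimated mean and SD (Lilliefors correction); the literal reading switches to Wilcoxon if either condition's values fail. Shapes and SDs were:
- Set A: person SD 7, difference SD 2.5; differences normal, t with 3 df, or centred lognormal (σ 0.6 and 0.8).
- Set B: person SD 8, difference SD 3; differences normal or centred exponential.
- Sex-gap runs: within-sex SD 5, half of each sex, gap in outcome units.

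**Formulas**
- Gate: D = max|Fₙ(x) − Φ((x − x̄)/s)|, failing if D > 0.1245 at n = 50.
- Paired t: t = d̄/(s_d/√n).
- Signed-rank: z = (W − n(n+1)/4)/√(n(n+1)(2n+1)/24). At n = 50 this is (W − 637.5)/√10731.25.

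**Step 1. Why outcome values hide the differences.** In set A, if the difference is independent of the uncovered value, the covered value has variance 7² + 2.5² = 55.25. The difference contributes 6.25/55.25 = 11%. Skewness carries over by the factor (2.5/√55.25)³ = 0.336³ = 0.038, so about 4% of it remains visible.

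**Step 2. How often the gate fires (set A, n = 50)**

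| Differences | Check on outcomes, either condition | Check on differences |
|---|---|---|
| Normal | about 9% | 5% |
| t, 3 df | 9-10% | 48-50% |
| Strongly skewed | about 9% | 96-97% |

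The 9% is simply two looks at 5%. Checking one condition only (set B), the rate is 4.9% for normal and 5.0% for skewed differences.

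**Step 3. Firing for an irrelevant reason.** With normal differences and a sex gap of 8, 12 or 16, the outcome check fires in 9%, 14% and 45% of trials; the check on differences stays near 5%. The rule's type I error remains 4.8-5.0%.

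**Step 4. Skewed differences with mean exactly zero (n = 50)**

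| Procedure | Rejects |
|---|---|
| Paired t, always | 6-8% |
| Rule as written (gate on outcomes) | 7.5-10.5%; up to about 18% with a 15-unit sex gap and strong skew |
| Wilcoxon, always | 19-33% |
| Rule with gate on differences | 20-33% |

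The two tests disagree in about 15-27% of these trials.

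**Step 5. Skewed differences with a real mean effect (set B, mean −1).** The pseudo-median of the centred exponential lies 0.163 SD from its mean. Here that is 0.163 × 3 = 0.49, so the mean is −1 but the pseudo-median is −1 + 0.49 = −0.51. Paired t rejects in 67.9% and Wilcoxon in 28.8%; they disagree in 39%. The rule gives 64.3% with the gate on outcomes and 29.4% with it on differences.

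**Step 6. No effect on anyone.** With randomised order, d is then a randomly signed period difference and so symmetric about zero. Giving the set A lognormal differences random signs, t rejects in 4.1-4.8%, Wilcoxon in 4.6-5.2%, and the rule in 4.2-5.3% under either gate.

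**The case against.** The case for leaving the rule alone is substantial, and parts of it stand.

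- **The rule is valid under no effect.** This stands (step 6). A reader might infer from the 19-33% that the plan has that false-positive rate for masks doing nothing. It does not. The figure arises only if Wilcoxon is always used or the gate sits on the differences, and only when the covering helps some people and harms others so that the mean is exactly zero. Even then, Wilcoxon is correctly rejecting its own hypothesis.
- **The authors may have meant the differences.** This is possible: the assumption referred to could be the paired t-test's own. A reader might infer that the outcome values were certainly intended, but the text names the outcomes without settling it. The charitable reading removes the first defect and enlarges the second, because skewed data are then mostly routed to Wilcoxon.
- **The algorithm is pre-specified.** Also true: both tests are named, and a reader should not infer that the analysis is left to discretion. What is not fixed is the target, nor which distribution triggers the switch.
- **The sex-stratified analysis could remove the sex-gap artefact.** It would if normality were checked within sex, but Data Analysis does not say so. Strata would then be smaller: at n = 25 with skewed, zero-mean differences, t rejects in 7.5% and Wilcoxon in 14.0%. The artefact needs a large gap, and alone it does not damage type I error.

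**Conclusion.** The point holds as a problem of what is estimated and reported, not as general inflation of type I error. As written, the gate carries almost no information about the assumption it is meant to protect. On the charitable reading, it lets the data choose between mean difference and pseudo-median, outcome by outcome.

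If the differences are roughly symmetric the practical effect is negligible: with normal differences and a shift of −1, power is 63.2% under the rule against 63.5% for t alone. If they are skewed, the choice of test can decide the conclusion.

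All sizes rest on assumed SDs, shapes and sex gaps, on the Lilliefors form of the test, and on the either-condition reading, because the documents give none of these. That the text does not name the differences, and that the two tests have different targets, does not depend on those assumptions. The change should be made before outcomes are compared by condition, but the point does not call the design into question.

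**What to change.** Change the Data Analysis wording as follows.

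1. Delete the normality gate. Moving it to the differences is not enough: with exponential-skewed, zero-mean differences that rule rejects in 21.9%, against 6.3% for the fixed t-test.
2. For VO₂ max, test duration and the other continuous outcomes, name one analysis of the within-person differences, either the paired t-test or an equivalent crossover linear model. Report the mean difference with its 95% CI.
3. Give the Wilcoxon signed-rank test on the differences, with the Hodges-Lehmann estimate, as a fixed sensitivity analysis for those outcomes. Inspect the differences or residuals graphically, without letting that change the main analysis.
4. Name one fixed test in advance for the ordinal Borg dyspnea and exertion ratings.
5. Reconcile Data Analysis with the sex-stratified within-subjects analysis promised in Research Design and Methodology, stating how sex enters the model or the reporting.

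The cost is text only. No visit, measurement or sample size changes, and no power calculation in the documents needs redoing.

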Specific Aim 3: Describe differences in outcomes between participants with and without previous history of COVID-19 diagnosis

Primary Outcomes:

- VO₂ max during CPET
- Test duration (time) on a CPET
- Reaction time (measured in milliseconds) and percentage accuracy on the SRT task

Secondary Outcomes:

- Minute ventilation (VE) at max during CPET
- Subjective dyspnea rating (Borg) during CPET
- Subjective exertion rating (Borg) during CPET
- O₂ saturation at baseline, each stage, and recovery during CPET
- Blood pressure at baseline, each stage, and recovery during CPET
- Max heart rate during CPET
- Respiratory quotient at max during CPET
- Blood lactate during CPET

[figure not shown]
INVESTIGATIONAL PLAN

Research Design and Methodology

Phase I:

In this prospective, randomized crossover trial of eligible athletes, we will compare VO₂ max during two maximal cardiopulmonary stress exercise tests (CPET), seven to ten days apart. Subjects will be randomized into either the face covering or non-face covering group using a 1:1 randomization scheme, stratified by sex, and will serve as their own control in the subsequent test seven to ten days later (see Figure 1. Randomization diagram, below). A within-subjects analysis will be performed stratified by sex.

[figure not shown]
Figure 1. Phase I Randomization diagram

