**Phase II:**

In this prospective, randomized crossover trial of 50 eligible participants, we will compare two maximal cardiopulmonary stress exercise tests (CPET) on a cycle ergometer, seven to ten days apart, and the impact on cognitive performance. ECG monitoring will take place during exercise testing among individuals with history of COVID-19. Subjects will be randomized into either the face covering or non-face covering group using a 1:1 randomization scheme, stratified by prior COVID-19 diagnosis, and will serve as their own control in the subsequent test (see Figure 2. Randomization diagram, below). A within-subjects analysis will be performed stratified by sex.

Cognitive testing will take place at the end of each stage of the CPET. Cognitive testing using the SACL Cognition application on iPad will include a baseline SRT measurement and additional measurements at the end of each stage of the CPET. The baseline will include a 30s session of SRT for familiarization and then a 30s session will be scored. SRT will then be administered for 30s at the end of each stage of the CPET. The SRT task includes a visual stimulus presented on the touchscreen. Subjects will be instructed to press the stimulus on-screen as quickly as possible. Reaction time and accuracy will be measured on the SRT task. Reaction time is calculated as the average amount of time in seconds between stimulus presentation and user response within a session. Accuracy is calculated as the total number of correct responses to stimuli divided by the total number of stimuli presented during a session (presented as a percentage).

Figure 2. Phase II Randomization diagram

Phase I: Eligibility Criteria

Inclusion Criteria	Rationale
18-29 years of age	Younger and older individuals are excluded to reduce variability of lung volume outcomes. Herdy, A. H. & Uhlendorf, D. (2010) Reference values for cardiopulmonary exercise testing for sedentary and active men and women. Sociedade Brasileira de Cardiologia.

Exclusion Criteria	Rationale
Orthopedic or neurologic, or other limitations	Individuals with limitations that would not allow for exercise testing on a treadmill are excluded.
Previous or current diagnoses for cardiopulmonary conditions	Individuals with conditions for which a healthcare provider has discouraged high-intensity exercise are excluded (e.g., arrhythmia, pacemakers, Wolfe Parkinson White syndrome).

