Phase I & II: Participants meeting the inclusion and exclusion criteria will be approached, screened, consented, and enrolled into the study. After obtaining informed consent, participants will be randomized to either complete their first test with no face covering or with a face covering in a 1:1 randomization ratio stratified by sex. A random number generator will be used to pre-determine the randomization group for each participant ID number. The group assignment will be not be revealed to either the participant or the study staff until informed consent is complete.

Cardiopulmonary Exercise Testing (CPET)

During the screening process, subjects will be encouraged to abstain from nicotine and caffeine prior to the test. Subjects will be scheduled to perform a CPET on a treadmill with (arm 1) and without (arm 2) a face covering (with testing for each arm seven to ten days apart). A face covering will be provided to participants randomized into the face covering group, with the option for participants to keep their face covering at the end of the assessment. Subjects will be fitted for metabolic testing (K5 CPET, COSMED, Concord, CA) equipment according to factory requirements. <https://www.cosmed.com/en/products/cardio-pulmonary-exercise-test/k5>

The use of new cloth face coverings beneath the K5 mask will be standardized, with face coverings consisting of the same material and cut/design for each participant (which the participant then keeps or discards). The correct fitting and leak tightness will be confirmed before each test for each subject. This will be achieved through (a) inspiration and (b) expiration with maximal force. During both maneuvers, the valve of the mask is closed leading to abrupt stop of the air flow. The fitting is carefully checked for the absence of any acoustic, sensory or visual indication of leakage (e.g., lifting of the mask, whistling or lateral airflow) by the investigators and the test person.

Phase I CPET Procedures:

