The study staff (PI, Co-Investigators, research coordinators and assistants) will be responsible for collecting and recording all clinical data. As results are collected, all Adverse Events will be identified, graded for severity and assigned causality, reported to the IRB, and compiled for periodic review. After assigning causality, the PI will decide the course of action for the study participant. The PI will evaluate all Adverse Events and determine whether the Adverse Event affects the risk/benefit ratio of the study and whether modifications to the protocol or informed consent form are required. An electronic regulatory binder in REDCap will be used to manage study logs and regulatory documentation. Throughout this process, the PI will inform and collaborate with the research team. The plan to monitor participant data and safety will specifically include the following: (1) [name] will inspect collected data; (2) The IRB offices will be contacted if there is an Adverse Event due to participation; (3) the research protocol will be revised if it is determined that the protocol or intervention presents an unforeseen risk to participants; (4) if an event occurs that requires immediate attention and [name] is unavailable, then members of the research team will follow the emergency procedures put in place by the research team, which may include calling emergency medical services; (5) an invitation to BSW Research Institute Quality Assurance will be delivered to conduct a site visit for internal auditing of procedures and documentation.

Study Withdrawal

Subjects may voluntarily discontinue participation in the study at any time, for any reason.

Protocol Deviations

All protocol deviations will be recorded in the participant's chart and electronic regulatory binder (REDCap) as they occur, and subsequently formally to the IRB at continuing review.

Data Analysis

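### Both phases are two-period crossovers, but the planned paired tests ignore period: a visit-to-visit change would cost precision, and would shift the estimate if the sequences end up unequal

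*Combined protocol and SAP*

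**What the plan says.** Phase I compares "two maximal cardiopulmonary stress exercise tests (CPET), seven to ten days apart". The Phase II design text opens "In this prospective, randomized crossover trial of 50 eligible participants" and uses the same interval between tests on a cycle ergometer. What is randomised is the order of the two conditions.

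- **Analysis (Data Analysis).** For the primary outcomes, "paired t-tests will be used to determine if there is a difference between participants when wearing and not wearing a face covering" if normality holds, and Wilcoxon signed-rank tests if it does not. Secondary outcomes follow the same plan. The only other statement on analysis, in Research Design and Methodology, is that a within-subjects analysis will be stratified by sex. No period, sequence or carryover term is mentioned.
- **Normality check (Data Analysis).** VO₂ max and test duration "will first be assessed for normality using a Kolmogorov-Smirnov test prior to determining the analysis to be used".
- **Allocation (Randomization, both phases).** The first test is done "with no face covering or with a face covering in a 1:1 randomization ratio stratified by sex". On the method: "A random number generator will be used to pre-determine the randomization group for each participant ID number". Blocks or another restriction are not described.
- **Phase II stratification (Research Design and Methodology).** Here participants are "stratified by prior COVID-19 diagnosis, and will serve as their own control in the subsequent test", which is a different factor from the one in the Randomization section.
- **Withdrawal (Study Withdrawal).** "Subjects may voluntarily discontinue participation in the study at any time, for any reason".

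**The concern.** In a two-period crossover the mask-minus-no-mask difference of a person who wears the covering second contains the visit-2 minus visit-1 change with a plus sign. For a person who wears it first, the sign is minus. A paired test treats this known, systematic pattern as random scatter.

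Two things follow if such a change exists. The standard error is inflated, so intervals are too wide and power is lost. And if the numbers of complete pairs differ between the sequences, the pluses and minuses do not cancel, so part of the visit effect is reported as a mask effect.

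A visit effect cannot be ruled out from the documents. No practice exercise test is described; only the Phase II reaction-time task has a short familiarisation session. Test duration, Borg ratings and reaction time all depend on effort or familiarity.

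A smaller, separate point: the normality check is worded for the outcomes themselves, whereas the paired t-test rests on the within-person differences.

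**Working it through.** The documents give no power, effect size, SD or visit effect, so there is no stated calculation to reproduce.

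**Inputs from the documents.** 50 participants per phase; 1:1 allocation; significance level 0.05 (taken as two-sided).

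**Assumptions.** σ is the SD of the paired differences within a sequence. π is the visit-2 minus visit-1 change, taken as 0, 0.25, 0.5 and 1σ. The true mask effect δ is 0 (for type I error) or 0.4σ (for power).

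**Model.** Each paired difference is d = δ + sπ + e, with s = +1 if the covering is worn second, s = −1 if first, and SD(e) = σ. Let N = n₁ + n₂, where n₁ is the covering-second sequence, and f = (n₁ − n₂)/N.

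- Paired estimate: expected value δ + fπ. The SD that the test uses is about √(σ² + π²(1 − f²)N/(N − 1)).
- Period-adjusted estimate: the average of the two sequence means, with standard error 0.5σ√(1/n₁ + 1/n₂) and N − 2 degrees of freedom. Its expected value is δ for any π and any split.

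**Balanced split, 25:25 (f = 0).** There is no shift. For π = 0.5σ the SD used is √(1 + 0.25 × 50/49) = 1.120σ, so the estimated standard error is 1.120/√50 = 0.158σ, against 0.5√(1/25 + 1/25) = 0.141σ with a period term. Simulation results:

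| π | Paired-t type I error | Paired-t power | Power with period term | Paired CI half-width | Half-width with period term |
|---|---|---|---|---|---|
| 0.25σ | 4.3% | 0.77 | 0.79 | 0.292σ | 0.283σ |
| 0.5σ | 2.9% | 0.72 | 0.79 | 0.317σ | 0.283σ |
| 1σ | 0.6% | 0.49 | 0.79 | 0.402σ | 0.283σ |

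The true standard error of the paired estimate stays at 0.141σ here; only its estimate is inflated, so the test is conservative. The signed-rank test behaves the same way: power 0.755, 0.685 and 0.432, against 0.77 for a rank-sum test on period differences.

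**Simple randomisation, averaged over splits.** Bias is 0 and type I error 4.9–5.0%. Power is 0.767, 0.699 and 0.499, against 0.78 with a period term. In this setting the true standard error also rises: 0.146, 0.158 and 0.200σ, against 0.143σ.

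**Given the split obtained.** The shift is fπ.

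| Split | f | Shift at π = 0.25, 0.5, 1σ | Paired-t type I error |
|---|---|---|---|
| 28:22 | 6/50 = 0.12 | 0.03, 0.06, 0.12σ | below 5% throughout |
| 30:20 | 10/50 = 0.20 | 0.05, 0.10, 0.20σ | 5.7%, 7.0%, 8.7% |
| 25:20 (five withdraw from one sequence) | 5/45 = 0.11 | 0.03, 0.06, 0.11σ | 4.7%, 3.9%, 2.1% |

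Without blocks, the chance of 30:20 or worse is 2 × P(X ≤ 20) for X ~ Binomial(50, 0.5), which is 0.203. Exactly 25:25 has probability 0.112.

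**Cost of adjusting when π = 0.** Power goes from 0.792 to 0.791 at 25:25, and from 0.792 to 0.775 at 30:20.

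**The case against.** Randomising the order already protects the comparison: on average there is no bias and the type I error is nominal. The size of the loss rests on assumed values of π and δ. At π = 0.25σ the loss is negligible, and nothing in the documents points to a visit effect as large as 1σ. The 7–10 day gap is meant to allow recovery, and the reaction-time task has a familiarisation session. Stratification usually implies blocks, and the randomisation diagrams (Figures 1 and 2), not readable in the text reviewed, might show planned numbers per sequence. Five withdrawals at random from 25:25 would all fall in one sequence only about 5% of the time, and even then the type I error stays below 5%.

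Much of this stands. The planned test is valid on average, error inflation needs a split somewhat wider than 28:22, and the consequence cannot be sized from the documents. But randomisation neither recovers the lost power nor removes the shift in the one split actually obtained. The recovery interval does not address learning or pacing between the two tests. Blocking, if intended, should be stated. None of these points puts a period term into the analysis.

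It is also fair that a model with one random participant effect suits outcomes with a single value per visit. Blood pressure, oxygen saturation and reaction time recorded at each stage would need a stage term or a per-visit summary.

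**Conclusion.** The concern holds. The plan randomises order and then does not use it. This is an avoidable loss of efficiency and of protection against an unlucky split, not an invalid test. At 25:25 the power loss is about 2 points if the visit effect is 0.25σ, 7 points at 0.5σ and 30 points at 1σ. If the split is 30:20, a fifth of the visit effect appears as a mask effect and the conditional type I error reaches 5.7–8.7%. These sizes rest on an assumed visit effect of 0.25–1σ, an assumed mask effect of 0.4σ, normal differences and 50 complete pairs; the 20% chance of a 30:20 or wider split assumes no blocking. With no visit effect, nothing material is lost under either analysis. The change should be made because it is cheap and the plan documents no power margin to absorb the loss.

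**What to change.** 1. Replace the paired tests with a mixed model for each outcome: fixed effects for condition, period and sequence, and a random participant effect. With complete pairs this equals comparing period differences between the two sequences; it also keeps participants who complete only one visit. It can be fitted by sex, or with a sex term, to respect the planned stratified analysis.
2. As the non-normal fallback, use a rank-sum test on period differences between sequences instead of the signed-rank test.
3. Judge normality on the residuals or the within-person differences.
4. State permuted blocks within stratum, after reconciling the Phase II stratification factor (prior COVID-19 diagnosis in Research Design and Methodology, sex in Randomization).

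The cost is a few lines of text and one degree of freedom. With no visit effect, the power given up is about 0.001 at 25:25 and 0.017 at 30:20. No new data or participants are needed.
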